12.0 STATISTICAL CONSIDERATIONS

12.1 Randomization and Stratification

No randomization or stratification of patients is planned for this study.

12.2 Populations for Analysis

The primary population for efficacy and safety will consist of the modified ITT population, i.e., patients who receive at least one dose of study drug and have any follow-up data.

The safety analysis population will consist of all patients treated with at least 1 dose of study drug. Safety data will be summarized by dose level, based on the original assigned dose of the study drug.

The efficacy analysis population for the primary and secondary efficacy endpoints will consist of all patients who have taken at least 1 dose of study drug and have had at least 1 post-baseline tumor assessment. Efficacy will be summarized by cohort.

The PK and PD analysis populations will consist of all patients who have received the requisite treatments and have data at the required time points. Any windows for timing of measurements will be specified in the statistical analysis plan.

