7.1 Overview of Study Design

This Phase 1b and 2a, open-label, multicenter study includes a dose-evaluation portion (**Part 1**) in which the safety profile and recommended Phase 2 dose (RP2D) of PLX9486 as a single oral agent administered daily in 28-day dosing cycles will be evaluated in patients with solid tumors (including GIST), followed by signal-seeking extension cohorts (**Part 2**) in which the following will be evaluated:

Part 2b. Open-label, sequential cohort dose-finding study of PLX9486 combined with PLX3397 in up to approximately 30 patients with solid tumors (including GIST) in a 3+3 design.

Part 2e. Open-label, sequential cohort dose-finding study of PLX9486 combined with sunitinib in up to approximately 30 patients with solid tumors (including GIST) in a 3+3 design.

A schematic overview of the study design is presented in [Figure 5](#).

Upon progression with single-agent PLX9486 treatment, a patient from Part 1 of the study may be rolled over to combination treatment of PLX9486 and either sunitinib or PLX3397 at the current dose or recommended phase 2 dose at the discretion of Medical Monitor and Principal Investigator (see Schedule of Events in [Attachment 5](#)).

The protocol is being amended (Amendment 7) to optimize the schedule of events and associated patient visits consistent with clinical experience in PLX121-01.

[figure not shown]
[figure not shown]

Figure 5: Overview of Study PLX121-01

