9.4.2 Holding of Study Drug

Study drug (PLX9486, PLX3397, and sunitinib) should be held at least 3 days prior to local radiation therapy either for pain palliation or to control slowly progressive disease. Study drug may be resumed 7 days after the completion of radiation therapy at the earliest provided that radiation related skin changes, if any, have resolved. Any AE related to radiation treatment that occurs up to and including 21 ± 7 days after administration of the last dose of study drug must be reported following instruction specified in [Section 13.2](#).

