11.0 STUDY ASSESSMENTS

Event schedules are summarized in [Table 1](#) (Part 1), [Table 2](#) [REDACTED] [Table 3](#) (Part 2b), [Table 4](#) [REDACTED] [Table 5](#) [REDACTED] [Table 6](#) (Part 2e), and [Table 7](#) [REDACTED]

All patients must provide written informed consent. During the consent process, the person obtaining consent must inform the patient of all elements of the study. No protocol-specific procedures, including Screening procedures, are to be performed until the patient has signed and dated an institutional review board (IRB)/independent ethics committee (IEC)-approved informed consent form. The study begins with the signing and dating of the informed consent form.

A patient will be considered enrolled in the study once all inclusion and exclusion criteria have been met, and the completed patient enrollment form has been submitted to Plexxikon Inc., signed by the appropriate representative, and returned to the investigative site.

Screening procedures are to be performed within 21 days before Cycle 1 Day 1 of study therapy. Each treatment cycle for Part 1, [REDACTED] 2b, [REDACTED] 2e, and [REDACTED] will be 28 days.

Dose interruptions in the middle of a treatment cycle will not affect the cycle and day count on the schedule of assessments. For example, if study drug is held on Cycle 1 Day 10, the following day should still be called Cycle 1 Day 11, etc. If a dose interruption occurs at the beginning of a new cycle, then the new cycle and day count will begin when study drug is restarted. For example, if study drug is held at the Cycle 2 Day 1 visit, then the day that the patient does resume dosing will be called Cycle 2 Day 1.

The end of the study for each patient is defined as the date of the last dose of PLX9486, PLX3397, or sunitinib (see [Section 10.4](#) for reasons for discontinuation or withdrawal of a patient from the study).

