12.4 Procedures for Handling Missing, Unused, and Spurious Data

All available efficacy and safety data will be included in the data listings and tabulations. No imputation of values for missing data will be performed.

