12.9 Safety Analysis

Safety variables to be assessed will include AEs, laboratory test results (hematology, clinical chemistry, and urinalysis), ECG, weight, and vital signs.

Adverse event terms recorded on the eCRFs will be mapped to prefer terms using the Medical Dictionary for Drug Regulatory Activities (MedDRA®) version 17.0 or later. All AEs will be summarized according to the system organ class and preferred term within the organ class. Adverse events will be tallied for overall frequency (number and percentage of subjects), worst reported severity, and relationship to study drug for each preferred term per subject. Serious adverse events will be similarly summarized. Listings of deaths, SAEs, and AEs leading to early termination of study treatment or premature withdrawal from study will also be provided.

Laboratory variables will be examined using mean change in value from baseline to scheduled time points. Laboratory values will also be categorized according to their CTCAE (version 4.0) toxicity grade and tabulated by worst on-study toxicity grade. The baseline value of a variable is defined as the last value obtained on or before the date and time of the first PLX9486 dose.

ECG, weight, and vital signs will also be summarized by changes from baseline to scheduled time points using descriptive statistics.

12.9.1 Part 1

The primary safety objectives of Part 1 are to evaluate the safety of orally administered PLX9486 and to establish the maximum tolerated dose/recommended Phase 2 dose (MTD/RP2D) in patients with advanced solid tumors (including gastrointestinal stromal tumor [GIST]).

12.9.2 [REDACTED]

[REDACTED]

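### Part 1 safety is grouped by original assigned dose with no cut-off when PLX3397 or sunitinib is added at progression, so per-subject worst-grade tables would count combination toxicity under single-agent PLX9486

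*Protocol*

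**What the plan says.** Section 12.2 places every treated patient in the safety population and then fixes the grouping: "Safety data will be summarized by dose level, based on the original assigned dose of the study drug".

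Section 7.1 allows a change of regimen after that assignment. On progression, "a patient from Part 1 of the study may be rolled over to combination treatment of PLX9486 and either sunitinib or PLX3397", and PLX9486 is then given "at the current dose or recommended phase 2 dose at the discretion of Medical Monitor and Principal Investigator". Both the regimen and the PLX9486 dose can therefore differ from the original assignment. Attachment 5 (Table 31) gives this phase its own visit schedule, with AEs, hematology, chemistry and ECGs still collected.

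Three further rules decide where those data go:

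- Section 12.4: "All available efficacy and safety data will be included in the data listings and tabulations".
- Section 12.9: AEs are tallied by overall frequency, "worst reported severity, and relationship to study drug for each preferred term per subject". SAEs are handled in the same way.
- Section 12.9: graded laboratory values are "tabulated by worst on-study toxicity grade". Baseline is the last value up to the first PLX9486 dose, with no reset at the add-on.

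Section 11.0 keeps the add-on phase on study: "The end of the study for each patient is defined as the date of the last dose of PLX9486, PLX3397, or sunitinib".

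**The concern.** AEs, laboratory values and ECGs are primary endpoints of Part 1, and Part 1 is meant to describe PLX9486 as a single agent. Section 5.10 relies on that description: it names the risk that PLX9486 enhances PLX3397 toxicity and says single-agent safety is evaluated in Part 1 to manage it.

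Both add-on drugs carry liver risk by the protocol's own account. Section 5.6.1 says PLX3397 hepatotoxicity may be fatal, and section 5.10 associates sunitinib with transaminase increases. Suppose, hypothetically, that a patient has a Grade 1 transaminase rise on PLX9486 alone and it becomes Grade 3 after a second drug is added. Under the rules above, that patient is one Grade 3 entry in the column for the single-agent starting dose. A reader of the table could not tell that the Grade 3 value arose on a combination.

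**Working it through.** The plan states no figure on this point, so there is none to reproduce. The check is a reading of the rules in sequence, followed by the size of one misplacement.

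**Step 1: are post-add-on data collected?** Yes. Table 31 schedules AEs and laboratory tests in the cycles after the add-on. Section 13.3 closes AE recording 30 days after the last dose of study drug or at new anticancer therapy. Section 9.4.2 treats all three agents as study drug ("Study drug (PLX9486, PLX3397, and sunitinib) should be held"), and section 11.0 dates the end of study from the last dose of any of them. Adding PLX3397 or sunitinib therefore does not appear to close the window.

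**Step 2: do they enter the tables?** Yes, under section 12.4, which excludes nothing.

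**Step 3: under which column?** Section 12.5 presents tables by part, and section 12.2 groups by original assigned dose. For a rolled-over patient, the original assignment is a Part 1 single-agent dose. No section moves the patient to Part 2b or 2e or opens an add-on column.

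**Step 4: which summaries merge the two phases?** Those that reduce a subject to one worst value: AE and SAE tallies by preferred term, and worst on-study laboratory grade. Section 12.9 summarizes ECG, weight, vital signs and mean laboratory change at scheduled time points. Table 31 counts its cycles from the added TKI, so those visits can be told apart.

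**Step 5: what is out of reach?** Section 9.3 limits DLTs to Cycle 1, before any add-on at progression. Section 5.5.1.1 gives an exposure (AUC) rationale for choosing the RP2D.

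**Step 6: size.** Cohort sizes come from Table 10: 3, 4, 3, 7 and 7, in total 24. If *k* patients in a group of *n* have their first or worst event after the add-on and would otherwise not count at that grade, the rate rises by *k*/*n*.

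| Group | n | Shift for k = 1 |
|---|---|---|
| 250 mg QD; 500 mg QD | 3 | 1/3 = 33.3 points |
| 350 mg QD | 4 | 1/4 = 25.0 points |
| 1000 mg QD; 500 mg BID | 7 | 1/7 = 14.3 points |
| All Part 1 | 24 | 1/24 = 4.2 points |

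The protocol does not give *k*, so it is an assumption. In a cohort of 7 with no true single-agent event, the displayed rate (exact 95% interval) would be:

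- k = 0: 0/7 = 0% (0 to 41.0%)
- k = 1: 1/7 = 14.3% (0.4 to 57.9%)
- k = 2: 2/7 = 28.6% (3.7 to 71.0%)

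**The case against.** The strongest reply is that section 12.2 fixes a dose grouping and no more. It does not say that this is the only summary, and it does not mention rolled-over patients. Treatment periods and phase-specific baselines are normally SAP matters, and the SAP is not available here. Section 9.4.2 is a rule about holding drug around radiotherapy, not a definition of study drug for tables. With 3 to 7 patients per cohort, the planned listings can be read patient by patient. Section 12.9 also tallies relationship to study drug, and the synopsis already describes experience alone and in combination.

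Part of this stands. A reader might infer that the plan forbids a separate add-on summary; it does not. A reader might also infer that all Part 1 safety output is mixed; the by-visit summaries need not be. Nor do the documents support the inference that the Part 1 dose decision is compromised, for the reasons in step 5. Section 9.4 does say later toxicity informs the RP2D, but the stated grounds for the Part 1 choice are exposure.

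The rest does not remove the point. The protocol is not merely silent: it states a grouping rule which, applied to a path it permits, puts the events in the wrong column. An SAP could supplement that rule, but it would have to do so explicitly. Relationship to study drug does not separate the phases, since the synopsis reports one SAE attributed to both PLX9486 and sunitinib. Listings help a careful reader but do not correct the table.

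**Conclusion.** The point holds for three outputs: the per-subject AE tally, the SAE tally and the worst-grade laboratory table of Part 1. Followed as written, they would count toxicity that first occurs or worsens after PLX3397 or sunitinib is added under the single-agent PLX9486 starting dose. One such patient is worth 14.3 to 33.3 points in a dose column and 4.2 points over all of Part 1.

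This rests on at least one patient having rolled over and having had a new or worse event afterwards. The documents do not show that this happened. The synopsis says patients are now being treated in Parts 2b and 2e only, which neither proves nor excludes earlier rollovers. It would go too far to say that the Part 1 safety results are in fact biased: the realized effect is unknown and may be zero. The change is worth making because it protects a primary endpoint and is cheap.

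**What to change.** In section 12.2, state that the Part 1 single-agent AE, SAE and worst-grade laboratory summaries end at the first dose of an added TKI. Report later events separately by combination regimen, against a baseline taken before the add-on. State how many Part 1 patients rolled over; if none did, one sentence saying so settles the matter. The grouping by original assigned dose can stay for the single-agent period.

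The cost is a little programming on dosing and event dates already collected. A patient can then appear under two regimens, which a footnote should say.

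The cut-off will not resolve attribution close to the switch, because an event soon after it may still reflect PLX9486 exposure built up beforehand. Table 14 gives geometric mean half-lives of 48.6 to 71.4 hours in healthy volunteers. Taking five half-lives as a convention, 5 × 48.6 h = 243 h, about 10.1 days, and 5 × 71.4 h = 357 h, about 14.9 days. Attribution therefore stays uncertain for roughly 10 to 15 days around the add-on, and the report should say so.

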Endpoints:	
Part 1:
 
The primary endpoints in Part 1 of the study include:
 
 Establish the MTD/RP2D of single-agent PLX9486 in solid tumors Safety endpoints (i.e., AEs, clinical laboratory evaluations, ECGs, physical examinations, and vital sign measurements) Pharmacokinetic (PK) analysis 
The secondary endpoints in Part 1 of the study include:
 
 ORR (RECIST 1.1) PFS DoR 
The exploratory endpoints of Part 1 of the study include:
 
 Biomarkers/KIT mutational analysis in peripheral blood and in archival tumor tissue 
Part 2:
 
[REDACTED]
 
[REDACTED]
 
The primary endpoints for Parts 2b and 2e of the study include:
 
 Establish the RP2D of PLX9486 in combination with PLX3397 or sunitinib Safety and tolerability 
The secondary endpoints for Parts 2b, e, of the study include:
 
 ORR (RECIST 1.1) CBR (Parts 2b, e) PFS OS 
[REDACTED]
 12 month OS rate 6 month PFS rate Duration of response (DoR) 
The secondary endpoints for Parts 2b, e, of the study include:
 
 Pharmacokinetics (PK)

	
The exploratory endpoints in Part 2 [REDACTED] of the study include:
 
• Biomarkers in peripheral blood and in archival tumor tissue• Tumor response in Part 2 cohorts by Choi criteria
Statistical Considerations	
The sample sizes of the different parts of the study are based on clinical rather than statistical considerations. The dose-escalation cohorts (Part 1 and Parts 2b and 2e) follow a typical 3 + 3 design. Data will be tabulated and evaluated by descriptive statistics.
 
[REDACTED]
 
[REDACTED]

Table 1: Trial Flow Chart – Part 1 (Single-agent PLX9486; 28-day Cycles)

STUDY DAY ▶ EVENT ▼	SCR	Cycle 1				Cycle 2				Cycle 3+ FU ²⁸	
		Day -21 to -1	Day 1 + 1 d	Day 2 ± 2 d	Day 8 ± 2 d	Day 15 ± 2 d	Day 22 ± 2 d	Day 1 ± 7 d	Day 15 ± 3 d	Day 1 ± 7 d	Other
Informed Consent	X										
Archival Tissue ¹	X										
Optional fresh tumor biopsy ²	X										
Demographics and Medical History	X										
Prior Treatment for Primary Malignancy	X										
Height	X										
Weight	X	X		X		X		X		X	
Physical Exam ³	X	X ⁴		X		X		X		X	
Hematology ⁵	X	X ⁴		X		X		X		X	
Chemistry ⁶	X	X ⁴		X		X		X		X	
Coagulation Tests (PT/INR and PTT)	X	X ⁴						X		X	
Tumor Markers ⁷	X	X ⁴						X		X	

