23 Screening radiographic assessment of tumor burden may be within 28 days of scheduled C1D1. After C1D1, radiographic assessment of tumor burden will occur approximately every 2 cycles (e.g., after Cycle 2, 4, 6) or more frequently as clinically indicated. After C5D1, radiographic assessment of tumor burden may be performed every 3 cycles (e.g., after Cycle 8, 11, 14) or more frequently as clinically indicated. Patients obtaining PET CTs on study do not also need separate CT scans, and disease can be followed via PET CT. The Sponsor may request copies of the scans and reports.

24 Drug diary to be reviewed and collected. Distribution of new drug diary. May be collected every 24 weeks ($+/-$ 7 days) from C5D1 on.

25 Review of concomitant medications must include all medications taken within 28 days prior to Screening.

26 AE monitoring both predoze and postdose on these days when PLX9486 is taken in the clinic.

27 This visit must occur \geq 30 days **after** last dose of PLX9486 and prior to starting any new anti-cancer therapy.

28 A post-study follow-up contact by phone by site staff will be conducted every 3 months during Year 1, then every 6 months thereafter to obtain information on any new anti-cancer therapy received, response, and survival status.

29 To be performed at Screening, every 2 cycles until C5, and then may be performed every 24 weeks ($+/-$ 7 days) from C5D1 on or more frequently as clinically indicated.

30 May be performed every 24 weeks ($+/-$ 7 days) from C5D1 or more frequently as clinically indicated.

Table 7:

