10.3 Treatment Group Assignments

This is an open-label, sequential dose-escalation study with extension cohorts. The initial dose level of PLX9486 will be 250 mg/day. Thereafter, dose-escalation groups will occur as described in [Section 9.2.1](#). Extension cohorts will be enrolled in parallel at the RP2D according to inclusion and exclusion criteria ([Section 8.1](#) and [Section 8.2](#)). The initial dose of PLX3397 will be 600 mg/day administered BID. Thereafter, dose escalation groups will occur as described in [Section 9.2.1.2](#). For the combination cohort with sunitinib the initial sunitinib dose will be 25 mg/day. Further details may be found in [Section 9.2.1.2](#).

10.4 Withdrawal of Patients from Drug Treatment or from the Study and Patient Replacement

The Plexxikon Medical Monitor will monitor safety data throughout the course of the study. The Medical Monitor will review SAEs within timeframes mandated by company procedures and will review trends, laboratory data, and AEs at periodic intervals and provide for interim safety analyses if appropriate.

The reasons a patient may discontinue or be withdrawn from the study include, but are not limited to, adverse event, clinically significant disease progression, patient request, investigator decision, protocol violation, patient noncompliance, and study termination by the Sponsor or institutional review board (IRB)/independent ethics committee (IEC). When a patient discontinues or is withdrawn, the investigator will notify the Sponsor and should perform the procedures indicated in the End of Study column in the Schedule of Events within 30 days after discontinuation of study drug and before initiation of any new anti-cancer therapy. Follow-up information will be obtained for patients who discontinue their participation in or are withdrawn from the study.

Patients withdrawn from the study for reasons other than toxicity or clinically significant disease progression (e.g., protocol violation or noncompliance) may be replaced at the discretion of the medical monitor and the investigator. Study drug administration may be discontinued due to an adverse event or at the discretion of the investigator.

The consequence of withdrawal of consent by a patient will be that no new information will be collected from that patient and added to the existing data or any database. However, every effort will be made to follow all patients for safety.

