12.7 Efficacy Analysis

12.7.1 Dose-escalation Cohorts (Part 1)

Secondary Endpoint:

The secondary endpoint of Part 1 is to evaluate the efficacy of PLX9486 in solid tumors as measured by ORR (by RECIST 1.1), duration of response (DoR), and progression-free survival (PFS). The ORR and the 2-sided, exact binomial 95% confidence interval for the ORR will be estimated. DoR and PFS will be estimated using the Kaplan-Meier method.

Statistical considerations (secondary endpoint): at the RP2D, if the observed overall response rate (ORR) is 17% (1 response of 6 patients), the 2-sided exact binomial 95% confidence interval for the true ORR is (0.4%, 64.1%). If the observed ORR is 33% (2 responses of 6 patients), the corresponding 95% confidence interval for the true ORR is 4% to 78%.

Exploratory Endpoints:

Descriptive statistics will be used to assess biomarkers in peripheral blood, in archival tumor tissue and in available tumor biopsies.

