12.7.2 Extension Cohorts (Part 2)

Primary Endpoints:

Clinical Benefit Response (CBR) is defined as SD at 16 weeks + PR + CR.

[REDACTED]

[REDACTED]

[REDACTED]

[REDACTED]

[figure not shown]
[REDACTED]

See [Table 28](#) for variations on sample sizes and response rates.

Parts 2b and 2e: Determine the safety and tolerability and establish the RP2D of PLX9486 in combination with PLX3397 or sunitinib.

Statistical considerations: The sample size of the different arms of the proposed escalation parts of the study were based on clinical rather than statistical considerations. The dose escalation cohorts (Part 1 and 2b and 2e) follow a typical 3 + 3 design. Data will be tabulated and evaluated by descriptive statistics.

Secondary Endpoints:

A list of secondary endpoints has been completely redacted with black bars of varying lengths.

Statistical considerations (safety and tolerability, CBR, ORR, OS, 12-month OS rate, PFS and 6-month PFS rate, DoR): descriptive statistics. The Kaplan-Meier method will be used to estimate the distributions of PFS, DoR, and OS.

[Table 28](#) below shows 2-sided exact binomial 90% and 95% lower and upper confidence limits (LCL and UCL) for the true response rate given various combinations of sample size and observed response rate.

Table 28: Two-sided Exact Binomial Confidence Limits for the True Response Rate

Sample Size	Number of Responders	Response Rate (%)	Observed CBR Rate			
			90% Confidence Interval		95% Confidence Interval	
			Lower (%)	Upper (%)	Lower (%)	Upper (%)
15	3	20	5.68	43.98	4.33	48.09
	4	26.7	9.67	51.08	7.79	55.10
	5	33.3	14.17	57.74	11.82	61.62
	6	40	19.09	64.04	16.34	67.71
	7	46.7	24.37	70.00	21.27	73.41
	8	53.3	30.00	75.63	26.59	78.73
	9	60	35.96	80.91	32.29	83.66

Exploratory Endpoints:

Parts 2 [REDACTED]. For each part, descriptive statistics will be used to summarize biomarkers in peripheral blood, in archival tumor tissue, and in tumor biopsies.

Tumor response will be evaluated in the Part 2 cohorts by Choi criteria ([Choi 2007](#)).

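### Section 12.2 gives two conflicting efficacy populations, and the more specific one drops treated patients who were never scanned from ORR, CBR, PFS and OS

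*Protocol*

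**What the plan says.** Three population statements in Protocol Section 12.2 bear on this point.

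- The opening one: "The primary population for efficacy and safety will consist of the modified ITT population", defined as at least one dose plus any follow-up data.
- The safety set: everyone who received at least one dose.
- The efficacy set, for the primary and secondary efficacy endpoints without exception: "all patients who have taken at least 1 dose of study drug and have had at least 1 post-baseline tumor assessment". Efficacy is to be summarised by cohort.

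The synopsis (Endpoints) introduces the Part 2b and 2e list with "The secondary endpoints for Parts 2b, e, of the study include". That list contains ORR, CBR, PFS, OS, the 12-month OS rate, the 6-month PFS rate and DoR. Part 1 has ORR, PFS and DoR as secondary endpoints. Section 12.7.2 states: "The Kaplan-Meier method will be used to estimate the distributions of PFS, DoR, and OS".

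On scan timing, Table 6 footnote 23 (Part 2e) says "radiographic assessment of tumor burden will occur approximately every 2 cycles (e.g., after Cycle 2, 4, 6) or more frequently as clinically indicated"; Tables 1 and 3 set the same initial interval. Section 10.4 gives reasons for leaving that include "adverse event, clinically significant disease progression, patient request, investigator decision". Section 12.4 says "All available efficacy and safety data will be included in the data listings and tabulations" and rules out imputation of missing values.

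**The concern.** The two efficacy definitions differ for any patient who was dosed and has some follow-up but no post-baseline scan. Neither is called supportive or tied to particular endpoints, so two analysts following Section 12.2 could report different results from the same data. The study is open-label, and the choice could be made after the outcomes are known.

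The more specific sentence is also the worse rule. It makes membership depend on something that happens after treatment starts. The patients it removes are early deaths, early toxicity exits, clinical progression without imaging, and withdrawals. Section 9.3 makes such cases realistic: patients who stop early for reasons other than DLT are replaced for DLT evaluability, and they have been treated but may never be scanned. OS needs no scan at all, because Section 7.3 collects survival status by telephone after treatment ends.

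**Working it through.** **The protocol's own figures.** With exact (Clopper-Pearson) limits, the lower limit is the α/2 quantile of Beta(x, n−x+1) and the upper limit is the 1−α/2 quantile of Beta(x+1, n−x).

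- Section 12.7.1, "if the observed overall response rate (ORR) is 17% (1 response of 6 patients": 1/6 gives 0.4% to 64.1%, as printed. The second example, 2/6, gives 4.3% to 77.7%, printed as 4% to 78%.
- Table 28: all seven rows at n = 15 reproduce (for example 3/15, 95% limits 4.33% to 48.09%).

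No printed figure is in dispute.

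**Who is lost.** Cycles last 28 days, so the first scheduled scan falls at about 2 × 28 = 56 days. A patient whose early progression is shown on an unscheduled scan stays in the set. A patient who leaves or dies before any scan does not.

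**Response rates.** An unscanned patient cannot be a CR or PR, nor SD at 16 weeks, so removal leaves the numerator unchanged and shrinks the denominator. With unscanned share d (not given in the protocol; assumed 5%, 10% and 20%), reported rate = true rate / (1 − d).

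- ORR of 20%: 0.20/0.95 = 21.1%; 0.20/0.90 = 22.2%; 0.20/0.80 = 25.0%.

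In counts, with exact 95% intervals:

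| Setting | All treated | Scan required |
|---|---|---|
| 30 patients, 3 unscanned | 6/30 = 20.0% (7.7 to 38.6) | 6/27 = 22.2% (8.6 to 42.3) |
| 30 patients, 6 unscanned | 6/30 = 20.0% (7.7 to 38.6) | 6/24 = 25.0% (9.8 to 46.7) |
| 15 patients (Table 28), 3 unscanned | 3/15 = 20.0% (4.3 to 48.1) | 3/12 = 25.0% (5.5 to 57.2) |
| 6 patients (Section 12.7.1), 1 unscanned | 1/6 = 16.7% (0.4 to 64.1) | 1/5 = 20.0% (0.5 to 71.6) |
| 6 patients (Section 12.7.1), 1 unscanned | 2/6 = 33.3% (4.3 to 77.7) | 2/5 = 40.0% (5.3 to 85.3) |

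**PFS.** Everyone retained in the scan-required set has survived to a scan, so the time before it is immortal. If every excluded patient failed before the landmark, an assumed true rate of 40% is reported as 0.40/(1 − d) = 42.1%, 44.4% or 50.0%. These are upper bounds.

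**OS.** Let s be the share of excluded patients alive at 12 months. Reported rate = (true rate − d·s)/(1 − d). With an assumed true rate of 60% and d = 10%:

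- s = 0: 0.60/0.90 = 66.7%
- s = 0.6: 0.54/0.90 = 60.0%
- s = 0.8: 0.52/0.90 = 57.8%

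The bias is upward if excluded patients do worse than average, which is likely but not certain.

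**DoR.** It is defined only in responders, all of whom have been scanned, so it is unaffected.

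**The case against.** The best reply is that the protocol already leans towards modified ITT. The opening sentence calls it primary, and Section 12.4 puts all available efficacy data into the tabulations. This does not settle the matter. The later sentence claims the same endpoints by name, and a promise to tabulate available data does not define a denominator. Parts of Section 12.7.2 are blacked out and could hold endpoint-specific rules for Part 2; Section 12.7.1 is readable and names none. A SAP could choose between the sets, but the contradiction would remain in the protocol.

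Three further points stand as limits:

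- The PFS figures are a ceiling. If a patient with no scan and no recorded death is censored at first dose (an assumption, since no rule is visible), keeping or dropping that patient leaves the Kaplan-Meier curve unchanged. Only pre-scan deaths, or clinical progression if it counts as an event, would move it, so the PFS effect can be as small as zero.
- Efficacy is summarised by cohort, and the cohorts in Tables 10 and 12 hold 3 to 8 patients. At that size the shift is small beside the interval width, and a cohort with no responders reads 0% either way.
- The endpoints are secondary and descriptive, and sample sizes rest on clinical grounds.

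These points limit the consequence. They do not remove the conflict.

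**Conclusion.** The concern holds. Section 12.2 fixes two incompatible efficacy populations. Following the more specific one removes treated, unscanned patients from ORR, CBR, PFS and OS.

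Under the assumed unscanned shares of 5% to 20%, a 20% ORR is overstated by 1.1 to 5.0 percentage points, which is modest against the exact intervals. PFS is probably overstated, by anything from nothing to the bounds shown. OS is likely overstated, but the direction is not guaranteed.

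No visible decision rule rests on these endpoints in Parts 1, 2b or 2e, so the primary objectives are not threatened. This is a reporting-validity problem that should be fixed. The main uncertainty is the number of unscanned patients, which the protocol does not give.

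**What to change.** In Section 12.2:

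- Name one efficacy population: all patients who received at least one dose of study drug.
- Count patients without a post-baseline scan as non-responders for ORR and CBR.
- Include all treated patients in PFS and OS from first dose.
- Keep the scan-required set only as a labelled sensitivity analysis for response.
- Delete the modified ITT sentence. This also removes its overlap with the all-treated safety population defined in the next paragraph.

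Keeping modified ITT and relabelling the scan-required set would also end the contradiction, but the any-follow-up condition would still select on what happens after dosing. One line in Section 12.4 should state that counting unscanned patients as non-responders is not imputation.

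The cost is wording only, with no new data or visits. The reported efficacy figures may be slightly less favourable.
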